10.2 Summary of analyses

Descriptive statistics will be used to present study data. Continuous variables will be presented as number of observations (n), mean, standard deviation (SD), median, minimum and maximum values. Categorical variables will be presented as counts and percentages.

Median time to the development of any AE will be determined using life-table analysis. All data will be presented separately by treatment group, local and systemic AEs. AEs and medical history will be coded using the most recent version of the Medical Dictionary of Regulatory Activities (MedDRA) preferred terms and will be grouped by system, organ, and class (SOC) designation.

Protocol number: DNDi-MILT COMB-01-PKDL

Protocol Version/Date: V3.0, 25 Feb 2020

Concomitant medications will be coded using the most recent version of WHO drug Dictionary.

Summary statistics will be provided by group including the frequency, severity, seriousness and relationship of AEs to each study drug organized by preferred term by SOC grouping.

Efficacy endpoints will be presented as summary statistics by treatment group and will be conducted once all subjects complete their initial cure assessment visit and the 12-months visit. The number of subjects who met the criteria for cure divided by the total number of subjects in that group will be presented by study group, and the correspondent 95% confidence interval. In addition, secondary efficacy endpoints will be described for the 24-months follow-up visit.

Subjects who are lost to follow-up will be compared to those completing the study with respect to study site, demographic, and clinical factors. If lost to follow-up exceeds 20% of the sample, attempts will be made to seek out these dropouts (or their proxies) to ascertain final outcomes. The attributes of people that are found through this process will be compared to those not lost to follow up.

For the pharmacokinetic data analysis, a population-based approach will be used employing non-linear mixed effects modelling (using NONMEM), to take into account within- and between-subject variability in all pharmacokinetic parameters, to optimally identify potential covariates such as body size descriptors (age, lean body mass, total body weight, etc) and other demographic parameters, but also interaction effects such as treatment-arm related differences in pharmacokinetics parameter estimates. The objective function value (equals -2 log-likelihood, derived from NONMEM) will be used to assess statistical significance of evaluated covariates and hierarchical structural models. The individual blood plasma:skin distribution ratio will be estimated using the developed pharmacokinetic model. Individual blood plasma:skin ratios of drug concentrations will be contrasted with the IC90 values previously obtained for L. donovani parasites.

10.3 Definition of study populations included in the analysis

For the primary analysis, an intention to treat (mITT) and per protocol (PP) analysis will be performed.

- Modified ITT population (mITT): all randomized patients receiving at least one dose of treatment. In case of error of treatment allocation, the actual treatment received will be used in the analysis. Modified ITT set of patients will be used in the primary and secondary efficacy analysis and in safety analysis.
- Per protocol population (PP): subset of patients belonging to the modified ITT and who did not have major protocol violations. Major protocol violations are any violation that may bias the result of the study, which will be defined a priori in the statistical analysis plan.

To take account of missing data, each of the above analysis sets (mITT and PP), the efficacy endpoints will be calculated in two ways: worst case scenario (missing outcome is defined as failure) and complete case analysis (missing outcome is excluded from the analysis, population is defined as set of completers).

• Set of completers: subset of patients belonging to the mITT or PP, who attended the 12 months follow-up visit. This set will be used in a sensitivity analysis of the primary

efficacy analysis.

A sensitivity analysis will also be performed for the secondary efficacy endpoints with the subset of patients who attended the 12 and 24-months follow-up visits.

Missing outcome data on the efficacy endpoints could arise if a patient withdraws consent, is lost to follow-up, or has an exam omitted by investigator oversight in patients who are not confirmed as cured.

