7.8 Rescue and Escape treatments

At any time-point during the study, if the patient does not respond to treatment, or lesions are worsening, or if after the healing period, the lesions reappear/reactivate, rescue treatment can be initiated at the discretion of the study investigator. A subject who receive rescue treatment at any time during the trial will be considered a treatment failure and will be withdrawn from the study. Rescue treatment will be provided to the patient as per standard recommendations by National Program with Miltefosine monotherapy for 12 weeks.

Patients will be given rescue treatment if:

- Progression of the disease is documented at any point in time during the study treatment or FU, and rescue treatment is indicated by the investigator
- They fail to tolerate trial medication or if occurrence of adverse event(s) during receipt of test drug dose (refer to the Ambisome[®] pack insert for withdrawing the patients) requires permanent interruption of treatment, and rescue treatment is indicated by the investigator
- If after healing period lesions reappear/reactivate

8 Study Assessments

8.1 Timing of Assessments:

Study assessments will be performed at baseline, D1, D8, D15, D22 (only for subjects allocated to combination arm), and D30 (EOT, +/- 3 days) during treatment phase.

All subjects will have follow-up visits at 3 months (+/- 7 days), 6 months (+/- 7 days) and 12 months (+/- 14 days) after the onset of treatment to assess efficacy and safety. A strategy will be put in place according to the context of each trial site to assure patients comply with the schedule of scheduled study visits. This will include active tracking of the patients through telephone contact or domiciliary visits.

In addition, a follow-up visit will be performed at 24 months (-1 month/+3 months) to assess the long-term response to treatment and safety. All patients will be invited to present to the 24 months follow-up visit, except those who have been withdrawn from the trial [e.g. for safety reasons (AE leading to treatment discontinuation and rescue treatment received), patients who withdrew consent, and cases of death, or patients who were treatment failure (received rescue treatment at any time during the 12 months follow-up period, including at 12 months visit).

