9.1 Rules in case of treatment suspension or interruption

In the event that treatment is interrupted (e.g. due to an adverse event), the decision to resume treatment will be taken by the site Principal Investigator. If miltefosine treatment is interrupted for more than 3 days and requires additional PKDL treatment (other than that described in the protocol) they will be considered a treatment failure for the purposes of the ITT analysis and excluded from the per protocol analysis. If interruption was for 3 or less days,

treatment will start again till the complete dose is administered.

Note that for the Ambisome[®] treatments, delay for >1 week of the administration of a dose which requires additional PKDL treatment (other than that described in the protocol), they will be considered a treatment failure for purposes of ITT analysis and excluded from the per protocol analysis. If interruption was for 6 or less days, treatment may start again at discretion of the investigator, until the complete dose is administered.

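### Section 10.3 defines the complete-case sets by visit attendance, so rescued patients, who are known failures but withdrawn, drop out and the completer cure rate is biased upward, most clearly at 24 months

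*Protocol*

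**What the plan says.** Section 10.3 of the protocol handles missing efficacy outcomes in two ways, for both mITT and PP. One is a worst case, with missing counted as failure. The other is a "complete case analysis (missing outcome is excluded from the analysis, population is defined as set of completers".

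The set of completers is then the "subset of patients belonging to the mITT or PP, who attended the 12 months follow-up visit", and its stated use is a sensitivity analysis of the primary efficacy analysis. For the secondary efficacy endpoints a sensitivity analysis is planned "with the subset of patients who attended the 12 and 24-months follow-up visits".

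The same section names three ways in which an outcome can be missing: withdrawn consent, loss to follow-up and an omitted examination. Rescue is not among them.

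On rescue, section 7.8 says that a patient who receives it at any time "will be considered a treatment failure and will be withdrawn from the study". Section 10.6 classes a patient for whom rescue is indicated as a treatment failure, without needing a 12-month assessment. Section 8.1 says: "All patients will be invited to present to the 24 months follow-up visit, except those who have been withdrawn from the trial". Its list of exceptions includes treatment failures rescued at any time in the first 12 months, the 12-month visit itself included.

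**The concern.** A patient with a missing outcome and a patient who did not attend are not the same thing here. A patient rescued at month 5 did not attend month 12, but the outcome is known: failure. Section 10.3 treats the two descriptions as one set. If the programming follows the attendance definition, patients leave the denominator because they failed.

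The complete-case result stands beside the worst-case result to show how much the missing data could matter. If known failures are deleted from it, part of the gap between the two figures is not due to missing data at all. The problem is sharpest at 24 months, where the question is durability and where non-invitation of rescued failures is written into the visit rules.

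**Working it through.** **The plan's own figure.** Section 10.1 gives 50 per arm for a precision of 10 points with a 95% CI at an 85% cure rate. With n = z²·p(1−p)/d², z = 1.96, p = 0.85 and d = 0.10, n = 48.98, so 49. The half-width at n = 50 is 9.9 points, so the stated 50 is reproduced. Adding 10% loss and 15% discontinuation as 50 × 1.25 = 62.5 gives the stated 63.

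**Who is in which set, by time of rescue**

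| Rescued | Outcome under 7.8 and 10.6 | 12-month completer set | 12-and-24-month set |
|---|---|---|---|
| Before the 12-month visit | Failure | Out (withdrawn) | Out (not invited) |
| At the 12-month visit | Failure | In (attended) | Out (not invited) |
| Between the two visits | Failure at 24 months | In | Out (withdrawn) |
| Not rescued, cure criteria unmet at the visit | Failure | In | In, if both visits attended |

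Every patient moved out by this rule is a failure at the time point concerned. None is a cure.

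**Size.** Let p be the cure rate among patients with a known outcome and s the share of failures rescued and withdrawn before the visit. The attendance-based rate is p / (1 − s(1 − p)). It equals p only when s = 0. At p = 0.85, s of 25%, 50% and 75% gives 88.3%, 91.9% and 95.8%.

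**Illustrative arm at 12 months.** 63 patients (section 10.1); 10% lost, so 6 missing and 57 known; 57 × 0.85 = 48.45, so 48 cured and 9 failures. Counting every known failure gives 48/57 = 84.2% (exact 95% CI 72.1 to 92.5), however many were rescued. Under the attendance rule:

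| Failures rescued before the visit | Rate | Shift (points) |
|---|---|---|
| 1 of 9 | 48/56 = 85.7% | +1.5 |
| 3 of 9 | 48/54 = 88.9% | +4.7 |
| 6 of 9 | 48/51 = 94.1% | +9.9 |

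The worst-case mITT rate is 48/63 = 76.2% in every row, because a rescued patient counts as a failure whether treated as known or as missing.

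**Why 24 months is worse.** Assume, for illustration, no relapse, late improvement or further loss after month 12. If 3 of the 9 failures are rescued before the 12-month visit and 3 more at it, the 12-month set gives 48/54 = 88.9% but the 24-month set gives 48/51 = 94.1%, against 84.2% when all known outcomes are kept.

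**What the share might be.** The protocol does not state s. The nearest figures are in section 1.4, from routine care at a different dose: 13.5% of patients lacked significant re-pigmentation at 12 months and 2% needed a second course. If the 2% is of all patients, 2/13.5 is about 15%, or 0.15 × 9 = 1.3 of 9 failures, close to the first row of the table.

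**The case against.** The best reply is that section 10.3 states the right principle: missing outcomes are excluded, and rescue is not listed as a cause of missingness. On that reading rescued failures stay in. This shows that the section contradicts itself. It does not settle which rule applies, since the same sentence equates the population with the attendance-defined completers and nothing places rescued patients back in it.

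Second, the affected analyses are sensitivity analyses in a non-comparative, descriptive trial, and no test or decision rule rests on them. That stands, and it limits the severity.

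Third, other parts of the plan give some protection. Section 10.2 compares patients lost to follow-up with completers, section 10.4 tabulates early terminations with reasons, and section 10.6 reports categories 1 and 2 without rescue through 24 months. So the complete-case analysis is not the only view of the problem, and an attentive reader could see the rescue withdrawals.

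Fourth, rescue is at the investigator's discretion, and many failures may first be declared at the 12-month visit. Those patients attended and remain in the 12-month set. Large shifts at 12 months are therefore possible but not shown to be likely. Moreover, non-invitation is written only for month 24; at month 12 the loss follows from withdrawal on rescue.

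A reader might also want to extend the point to the PP rule in section 9.1, which excludes patients whose interruption led to additional treatment. Whether the same interruption without additional treatment stays in PP cannot be told from the protocol, because section 10.3 leaves major violations to the SAP. The rule that analyses patients by treatment received is a separate matter with no upward direction, and of little consequence in a non-comparative trial.

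**Conclusion.** The point holds for the complete-case analyses, and it should be fixed. The direction is certain if the attendance definition is followed and any failure is rescued before the visit. The size is not known: in the illustrative arm it runs from +1.5 to +9.9 points for 1 to 6 of 9 failures rescued early, resting on 10% loss, about 85% cured among known outcomes and an assumed rescue share. At the upper end of that range the shift is about as large as the planned precision of 10 points.

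A reader might infer that the trial's main cure rate is inflated. The protocol does not support that, since the worst-case mITT result counts every rescued patient as a failure.

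**What to change.** In section 10.3, define the complete-case set at each time point as patients with a known outcome: the visit was attended, or treatment failure was declared at or before it. Patients in the second group count as failures. Use the same rule at 12 and at 24 months, so that a patient rescued at or before month 12 remains a failure in the 24-month analysis. Carry the definition into the SAP.

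This changes the wording of the two set definitions and needs no new data, because rescue and the declaration of failure are already part of the outcome definitions. The cost is a complete-case cure rate that will be lower, and so less favourable, whenever failures were rescued before the visit.

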10.4 Subject Disposition

The number of patients who were screened, failed screening, randomized, completed the treatment period, completed the follow-up, early terminations and reasons for early termination of study will be summarized by number of patients (n) and percentages (%).

10.5 Baseline

The continuous variables of the baseline and demographic characteristics will be summarized using number of patients (n), mean, SD, median, minimum and maximum. The categorical variable gender will be summarized using number of patients (n) and percentage. (%).

10.6 Efficacy Analysis

Efficacy of the treatment will be assessed at 12 and at 24-month follow-up visit. The efficacy estimate will be reported as proportion of cured with its 95% confidence interval.

The data will be analysed as proportion, according to either mITT or PP populations.

Definitions

- **Cure**: Complete resolution of papular and nodular lesions (flattening of 100% of lesions) and significant improvement (> 80% re-pigmentation, as per scoring system, section 8.3.1) of macular lesions at 12 or at 24 months follow-up visits.
- Treatment Failure:

A patient will be considered a treatment failure:

- If rescue treatment is indicated by the investigator due to:
 - Non-response to treatment or worsening of PKDL lesions anytime during the treatment phase of the study
 - Occurrence of adverse events that leads to treatment discontinuation and require rescue treatment
 - Relapse: patient presented clinical response/improvement of lesions, but in subsequent follow-up visits the investigator observes appearance of new lesions and/or worsening of PKDL lesions, and indicates rescue treatment at any-time during follow-up period, including 24 months visit.

Or

• Patient did not fulfil the criteria for cure at the 12 or 24-months follow-up: presenting persistence of papular or nodular lesions and/or not significant improvement (< 80% re-pigmentation, as per section 8.3.1) of macular lesions.

• Lost to Follow Up: Patient did not turn up for 24 month follow up assessment and could not be contacted by health educators.

In addition, the overall clinical presentation of the patient will be assessed by the Investigator using the following categories ³⁴:

- Category 1: All lesions have improved and the majority of lesions have resolved. Any remaining lesions are only faintly visible as re-pigmentation is almost complete.
- Category 2: The majority of lesions show significant improvement, some lesions have resolved
- Category 3: No new lesions, but the majority of lesions show no or slight improvement.
- Category 4: New lesions have appeared and there is no or little improvement of other lesions

The proportion of PKDL patients in category 1, 2, 3 and 4 with its 95% confidence interval will be summarized per study arm, at 12 and at 24 months follow-up visits.

The proportion of PKDL patients in categories 1 and 2 who did not require rescue treatment up to and including 24 months visit will be summarized for all patients included in the study and per study arm.

The proportion of PKDL patients in categories 1 and 2 with negative parasitology by microscopy at 12 and 24 months will be summarized for all patients included in the study and per study arm

The proportion of PKDL patients in categories 1 and 2 with negative parasitology by qPCR at 12 and 24 months will be summarized for all patients included in the study and per study arm

10.7 Safety Analysis

All patients enrolled and who have been started on study medication will be included in the safety analysis (treatment-emergent AEs). The AE and medical history data will be coded using MedDRA dictionary.

AE's will be tabulated by System Organ Class (SOC), severity (based on the CTCAE v4.03 see section 8.7.7), seriousness and by causal relationship to study drugs.

The proportion of patients with SAE, AESI and/or AEs leading to treatment discontinuation will be described per System Organ Class (using preferred terms defined by MedDRA) and summarised according to relationship to treatment and severity (CTCAE, version 4.03). In addition, a narrative for each of the SAE, AESI and AE leading to treatment discontinuation will be developed describing all aspects of the medical event.

The proportion of patients presenting at least one treatment emergent AE (TEAE) will be presented. All TEAEs will be described per study arm using the same classification as presented above. AEs will be tabulated by severity (CTCAE V4.03) and causality.

Abnormalities of laboratory/procedures results will be tabulated with respect to clinical significance. In addition, shift tables and graphs will be generated to describe the laboratory parameter values over time, per treatment arm.

10.8 PK Analysis

For the pharmacokinetic data analysis, a population-based approach will be used employing non-linear mixed effects modelling (using NONMEM), to take into account within- and between-subject variability in all pharmacokinetic parameters, to optimally identify potential covariates such as body size descriptors (age, lean body mass, total body weight, etc) and other demographic parameters, but also interaction effects such as treatment-arm related differences in pharmacokinetics parameter estimates. Separate PK models will be developed for miltefosine in plasma and for total amphotericin B in plasma. The objective function value (equals -2 log-likelihood, derived from NONMEM) will be used to assess statistical significance of evaluated covariates and hierarchical structural models. The individual blood plasma:skin distribution ratio will be assessed based on the end of treatment samples. Exposure estimates in the skin that follow from the pharmacokinetic analysis will be compared to the IC90 values previously obtained for *L. donovani* parasites.

10.9 PD Analysis

Quantitative qPCR data of parasite numbers will be used to estimate the time till negativity in skin snip, blood and tape disc samples and perform a survival curve analysis. Appropriate covariates, such as respective drug exposures and drug plasma:skin penetration ratio, will be evaluated to estimate the influence of these covariates on the parasite clearance in patients. If the quantitative data allow for it, other regression methods will be used to estimate the dynamics of parasite clearance in patients, which will be detailed in a separate post-hoc analysis plan.

10.10 Immunological parameters Analysis

The cytokines IL-2, IFNY, TNFα, IL-10, and Granzyme B (and possibly other biomarkers, after a preliminary screening) are secreted by T- cells after stimulation and will be measured in the stimulated whole blood supernatant by BD[™] Cytometric Bead Array Human Th1/Th2 Cytokine CBA.

Results for each cytokine will be expressed as the difference between the SLA stimulated concentration and the negative control plasma concentration. Levels of cytokines will be described over the different time-points at baseline, treatment and follow-up phases for the overall population, by treatment arm and by treatment outcome (cure vs failure at D210). Sub-group analysis for cytokines will be detailed in the Statistical Analysis Plan.

11 Data Safety Monitoring Board

A Data Safety Monitoring Board (DSMB), composed of at least 3 members independent of the investigator and sponsors, will be set up prior to study initiation. The DSMB will review the study data at pre-determined intervals and issue recommendations about the study. The data and intervals will be agreed prior to the study initiation and documented in the DSMB Charter.

12 Quality Assurance and Quality Control Procedures

12.1 Investigator's file

The investigator must maintain adequate and accurate records to enable the conduct of the study to be fully documented and the study data to be subsequently verified. These documents include Investigator's Site File, subject clinical source documents and screening / enrolment logs. The Investigator's Site File will contain the protocol/protocol amendments, CRF and query forms, IEC and regulatory approval with correspondence, sample informed consent, drug accountability records, staff curriculum vitae and authorization forms and other appropriate documents/correspondence etc.

